4 MEASUREMENTS OF STUDY VARIABLES AND DEFINITIONS OF OUTCOME VARIABLES

4.1 Screening and demographic measurements

The following data will be recorded via a standard CRF:

- Date of birth
- Height and weight (Body Mass Index)
- Sex
- Race
- Relevant medical and surgical history
- Medication
- Oral examination
 - Local condition of alveolus and adjacent teeth
 - Periodontal disease
 - Bone loss
 - Caries
 - Mobility
 - Crown
 - Post/core
 - Endodontic treatment
 - Existing periapical radiolucency
 - Tobacco use
 - Reason for tooth extraction (if known)
 - Duration of edentulous period (if known)
 - Previous bone graft, soft tissue graft, or apical surgery
 - Opposing tooth contact in maximum intercuspatation

4.2 Efficacy

Primary outcome variable

4.2.1.1 Dimensional osseous changes

The amount of horizontal and vertical bone changes will be calculated using data from DICOM images acquired by CBCT using 3D software.

4.2.1.1.1 Methods of assessment

CBCT images will be obtained at baseline (Visit 2) and 6 months following alveolar ridge augmentation (Visit 7). Using ITK-Snap 3D analysis software, the CBCT images will be aligned via superimposition of adjacent tooth structures to permit evaluation of bone changes within the bound edentulous space. One masked analyst will complete the evaluations.

4.2.1.1.2 Derivation or calculation of variable

The mid-alveolar point positioned on a tangent drawn from the mesial and distal adjacent tooth CEJs will be used as a reference point for assessment of dimensional bone changes in the Z-axis (bone width) and Y-axis (bone height). The changes in the bone dimensions between baseline (Visit 2) and 6 months (Visit 7) will be measured. The change for each study site will be compared longitudinally and the average for each treatment group will be calculated and compared among treatment groups.

Secondary outcome variables

4.2.1.2 Inflammation

The presence or absence of soft tissue inflammation in the area of ridge augmentation will be visually assessed.

4.2.1.2.1 Methods of assessment

Soft tissue erythema within 3 mm from the crestal incision in the edentulous site will be visually assessed at post-operative evaluations (Visits 4-6).

4.2.1.2.2 Derivation or calculation of variable

Erythema will be marked as either present or absent according to the clinician's judgment. The percentage of sites with or without inflammation will be calculated for each treatment group and compared longitudinally.

4.2.1.3 Infection

The presence or absence of infection in the area of ridge augmentation will be assessed through visual evaluation and palpation.

4.2.1.3.1 Methods of assessment

Infection will be assessed at post-operative evaluations (Visits 4-6). The presence of suppuration from the crestal incision or soft tissues adjacent to the localized ridge augmentation will be assessed through visual evaluation. Fluctuance in the area of the augmentation will be assessed through gentle palpation of the surgical site. (Visits 4-6).

4.2.1.3.2 Derivation or calculation of variable

Infection will be marked as either present or absent according to the clinician's judgment. The percentage of sites with or without infection will be calculated for each treatment group and compared longitudinally.

4.2.1.4 Soft tissue complications

The presence of soft tissue complications, including wound exposure or soft tissue dehiscence, will be visually assessed.

4.2.1.4.1 Methods of assessment

At each post-operative evaluation (Visits 4-6), the presence of membrane exposure or soft tissue dehiscence will be visually assessed.

4.2.1.4.2 Derivation or calculation of variable

Membrane exposure or soft tissue dehiscence will be marked as either present or absent according to the clinician's judgment.

4.3 Patient reported outcomes

Not applicable

4.4 Health economic measurements and variables

Not applicable

4.5 Pharmacokinetics

Not applicable

4.6 Safety measurements and variables

The methods for collecting safety data are described below.

Adverse Events

4.6.1.1 Definitions

The definitions of AEs, ADEs and Serious Adverse Events (SAEs) are given below. It is of the utmost importance that all staff involved in the study are familiar with the content of this section. The principal investigator is responsible for ensuring this.

Adverse Event

An AE includes any unfavorable and unintended sign, symptom, syndrome or illness that develops or worsens during the period of observation in the clinical study. For the purposes of this study, adverse events which are considered related to the GBR procedure or related to the GUIDOR membrane will be reported. Adverse events which are not related (temporal relationship of the onset of the event, relative to the use/administration of the medical device, is not reasonable or another cause can itself explain the occurrence of the event) will not be required to be reported.

For the purposes of this protocol, the following occurrences are considered to be expected observations following guided bone regeneration procedure and will not be captured as additional complications or device related adverse events:

- Post-operative nausea determined to be procedure related or due to reactions to pain medication
- Post-operative transient headache or pain responding to standard medications
- Post-operative pain related to procedure within 7 days
- Post-operative swelling related to the procedure and determined not to be

associated with infection within 7 days of procedure.

Adverse Device Effect

An ADE is any untoward and unintended response to a medical device. This definition includes any event resulting from insufficiencies or inadequacies in the instructions for use of the medical device or any event that is a result of a user error. This definition also includes treatment- or procedure-related events. ADEs can only occur from the time of medical device use/administration. Here the event is related to the use of the medical device where there is a probable/definite relationship that the event may have been caused by the medical device, or treatment.

- Probably related: temporal relationship of the onset of the event, relative to the use/administration of the medical device, is reasonable and the event is more likely explained by the medical device/treatment than by any other cause.
- Definitely related: temporal relationship of the onset of the event, relative to the use/administration of the medical device, is reasonable and there is no other cause to explain the event.

Serious Adverse Event

A SAE is an AE/ADE occurring during any study phase of the medical device that fulfills one or more of the following criteria:

- Results in death
- Is immediately life-threatening
- Requires in-subject hospitalization or prolongation of existing hospitalization
- Results in persistent or significant disability or incapacity
- Is a congenital abnormality or birth defect
- Is an important medical event that may jeopardize the subject or may require medical intervention to prevent one of the outcomes listed above

For the purposes of this study, all Serious Adverse Events will be reported.

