Bio-Gide® membrane is a porcine type I/type III non-cross-linked collagen bilayer membrane. The membranes are resorbed via collagenase over a 24 week period. The dense outer surface faces soft the overlying soft tissues, preventing epithelial or fibrous tissue ingrowth. The porous inner surface faces the bone and/or bone graft material and permits osteoblast ingrowth.

Mineralized freeze-dried cortical bone allograft (LifeNet Health) is a particulate bone graft material. It has a particle size of 250-1000 µm and is sterilized via Allowash XG® technology.

Duration of treatment

The study follow-up will be approximately 6-7 months. The treatment period includes guided bone regeneration in anticipation of future dental implant care. Follow-up visits following the guided bone regeneration will occur at 7 days, 14 days, 28 days, 6 months.

Outcome variables

Efficacy

Primary outcome variable:

- Horizontal and vertical bone changes at 6 months

Secondary outcome variables:

- Inflammation (refer to 4.2.2.1) or infection (refer to 4.2.2.2)
- Membrane exposure
- Soft tissue complications (refer to 4.2.2.3)

Patient reported outcomes

- Not applicable

Health economics

- Not applicable

Pharmacokinetics

- Not applicable

Safety

- Summarize all adverse events

Genetics

- Not applicable

Statistical methods

The primary outcome variables of dimensional horizontal and vertical bone changes will be analyzed by Wilcoxon rank sum test.

The secondary outcome variables assessing the presence or absence of inflammation, infection, and soft tissue complications (wound dehiscence, membrane exposure) will be analyzed by chi-square test.

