3.4 Method of assigning subjects to treatment groups

Subject numbers (subject ID) will be consecutively allocated in series at day of inclusion (Visit 1). Subjects at center 1 will receive numbers starting at 101 and subjects at center 2 will receive numbers starting at 201. Enrollment will continue until 30 subjects at each center have been allocated a subject ID. If a subject discontinues, the subject number will not be reused.

Subjects will be randomized at day of alveolar bone regeneration (Visit 3). At Visit 2 all study sites in all subjects are considered equivalent. The randomization schedule will be generated using a validated computerized randomization system under the responsibility of the investigatory team. The randomization assignment will be concealed via envelope until the surgical date. Randomization will be stratified by center and smoking habit, i.e. each center will have 10 subjects in each group A, B and C, respectively with an equal number of subjects with current tobacco consumption per group. Each subject will be treated according to the treatment code in the envelope. The allocation will be revealed to the clinician only following flap elevation for the alveolar regeneration procedure.

The randomization code envelopes will be stored at each center by designated research staff.

Pre-study, concomitant and post-study treatment(s)

Systemic corticosteroids or any other medication that would compromise post-operative healing and/or bone healing are not allowed.

After surgery, mouth rinsing with 0.12% non-alcohol chlorhexidine rinse will be subscribed according to local routines.

Subjects will be given post-surgical instructions with regards to diet and oral hygiene. Oral hygiene instructions will be given to the subjects at all study visits.

Other medication, which is considered necessary for the subject's safety and well-being, may be given at the discretion of the investigator(s). The administration of all medication (excluding dietary supplements) must be recorded in the appropriate sections of the CRF.

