4.6.1.2 Recording of Adverse Events and Adverse Device Effects

At each visit, the subject will be asked an open question; "Have you had any health problems since the previous visit?"

All health problems, reported by the subject or found at the clinic visit, where the investigator believes the event to be related to the investigational medical device or treatment, must be recorded in the CRF as AEs, specifying time of onset, action taken, outcome and whether it constitutes a SAE or not.

Should a pregnancy occur, it must be reported in accordance with the procedures described in Section 9.2, Pregnancy. Pregnancy in itself is not regarded as an AE unless there is a suspicion that a medical device under study may have interfered with the effectiveness of a contraceptive medication.

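### Non-serious adverse events must be recorded only if already judged related, under overlapping causality definitions, although the synopsis promises a summary of all of them

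*Combined protocol and SAP*

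**What the plan says.** - **Safety outcome.** The protocol synopsis, under outcome variables, says: "Summarize all adverse events".
- **Definition of an adverse event.** Section 4.6.1.1 sets no causality condition: "An AE includes any unfavorable and unintended sign, symptom, syndrome or illness that develops or worsens during the period of observation".
- **Reporting rule.** The same section then narrows what is reported: "adverse events which are considered related to the GBR procedure or related to the GUIDOR membrane will be reported". Unrelated events are exempt. They are identified by the timing of onset relative to the device or by an alternative cause, in a sentence that ends "is not reasonable or another cause can itself explain the occurrence of the event) will not be required to be reported".
- **Probably related.** Under Adverse Device Effect, the timing "is reasonable and the event is more likely explained by the medical device/treatment than by any other cause". Definitely related requires reasonable timing and no other cause. No other level of relatedness is defined.
- **Recording rule.** Section 4.6.1.2 covers health problems "where the investigator believes the event to be related to the investigational medical device or treatment, must be recorded in the CRF as AEs".
- **Expected events.** Section 4.6.1.1 lists post-operative nausea, headache, pain and swelling, under stated conditions, as not captured.
- **Serious events.** Section 4.6.1.1 requires all of them to be reported, with no relatedness condition.
- **Knowledge of the arm.** Section 3.4: "The allocation will be revealed to the clinician only following flap elevation for the alveolar regeneration procedure". The only masking described is that of the CBCT analyst (section 4.2.1.1.1).
- **Analysis.** Section 6.1 provides descriptive statistics for each variable. Section 6.2 names no test for adverse events.

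**The concern.** Causality is being used as an entry condition for the data. It would normally be an attribute recorded about each event. An event that is never written down cannot be recovered at analysis, and a reader of the final table cannot tell how many were left out or on what grounds.

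Three features make the filter unreliable. Its definitions can classify the same event in two ways. Its wording does not treat the study materials alike. And the call may be made by someone who knows which membrane and graft the subject received. Two centers, or two arms, could therefore apply it differently. The resulting table would be neither a count of all adverse events, as the synopsis promises, nor a consistently defined set of related ones.

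**Working it through.** The plan states no adverse event rate or safety calculation, so there is no figure of its own to reproduce here. The check is mainly a comparison of the text.

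**1. From event to summary.** The definition admits any untoward event. The reporting rule keeps those attributed to the surgery or to GUIDOR. The CRF rule keeps those the investigator believes related. The expected-event list removes more. A summary built on what must be recorded is therefore a subset of what the synopsis names.

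**2. The definitions applied to possible events.**

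| Timing | Other cause | Device or treatment most likely? | Class under 4.6.1.1 |
|---|---|---|---|
| Not reasonable | Any | – | Not related, exempt |
| Reasonable | None | Yes | Definitely related, reportable |
| Reasonable | Sufficient on its own | Yes | Not related **and** probably related |
| Reasonable | Sufficient on its own | No | Not related, exempt |
| Reasonable | Present, not sufficient on its own | No | No class defined |

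The third row is the overlap. The not-related test asks only whether another cause could explain the event; the probable test asks which cause is more likely. Both can be true at once. The last row is a gap.

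**3. Wording by arm.** Group A receives GUIDOR and allograft, group B GUIDOR alone, and group C Bio-Gide and allograft. The reporting rule in 4.6.1.1 names the procedure and GUIDOR only. Read literally, an event attributed to Bio-Gide or to the allograft is reportable only through the procedure. Section 4.6.1.2 refers more broadly to the investigational device or treatment. The two rules do not match.

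**4. Which events depend on the filter.** Inflammation, infection, membrane exposure and dehiscence are scored present or absent at scheduled visits with no relatedness condition (section 3.1, Table 1 and section 6.2), and serious events are all reported. What remains is non-serious events outside those four outcomes (section 3.2 mentions thermal sensitivity, for example) and events that arise and resolve between visits. The longest interval runs from day 28 to week 24: 24 × 7 − 28 = 140 days without a scheduled visit. An event confined to that interval reaches the CRF mainly through the open health question, and so through the filter.

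**5. Illustration, with assumed rates.** Section 6.3 gives 20 per group: 18 / (1 − 0.10) = 20. Let p be the true proportion of subjects with an event, equal in two arms, and a the proportion of those recorded. Subjects recorded = 20 × p × a.

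| p (true number) | a: 50% vs 50% | 60% vs 40% | 80% vs 40% | 90% vs 50% |
|---|---|---|---|---|
| 20% (4) | 2.0 vs 2.0 | 2.4 vs 1.6 | 3.2 vs 1.6 | 3.6 vs 2.0 |
| 40% (8) | 4.0 vs 4.0 | 4.8 vs 3.2 | 6.4 vs 3.2 | 7.2 vs 4.0 |
| 60% (12) | 6.0 vs 6.0 | 7.2 vs 4.8 | 9.6 vs 4.8 | 10.8 vs 6.0 |

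For example, 4 × 0.9 = 3.6 of 20 (18%) against 4 × 0.5 = 2.0 of 20 (10%), with no true difference. With equal recording there is no difference between arms, but the rates are understated. Neither p nor a comes from the documents.

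**The case against.** The strongest reply is that little is at stake. The soft-tissue outcomes that matter most are collected whatever their cause. Many events one might fear losing would be caught there: a draining tract is suppuration, a fluctuant swelling is infection, and a slough that opens the wound is dehiscence. This stands, and it sets the limits of the point.

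Second, every arm has the same flap and regeneration surgery, so a surgical-site event can be recorded as procedure-related without blaming any material. This makes a difference between arms less likely. It does not remove the exemption for events with another sufficient cause, nor the mismatch between 4.6.1.1 and 4.6.1.2. Likewise, smoking is a ready alternative cause, but randomization is stratified by it, so it is more likely to lower recorded rates generally than to tilt them.

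Several stronger readings are tempting and are not supported:

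- *That the synopsis promise cannot be kept.* Unrelated events are not required to be reported; recording them is not forbidden. The rules fail to assure a complete summary, and optional recording invites inconsistency between centers.
- *That every possibly related event is exempt.* The exemption needs unreasonable timing or a sufficient alternative cause. Other doubtful events simply have no class.
- *That a between-arm safety test is biased.* None is planned; only descriptive summaries are.
- *That the assessor is known to be unmasked.* The protocol says the clinician learns the arm. It does not say who judges causality, or that this person is masked.
- *That the trial's soft-tissue evidence is undermined.* The scheduled outcomes do not pass through this filter.

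**Conclusion.** The point holds within limits. The rules for recording non-serious adverse events do not assure the summary that the synopsis names. The not-related and probably-related definitions overlap, a possible relation has no level, and the two recording sections describe the study materials differently. These are facts of the text and need no assumption.

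That recording could differ by arm or center is an inference. It rests on the clinician knowing the allocation and on no masked assessor being described. Its size is unknown and may be nil. The part of the trial affected is the descriptive summary of non-serious events outside the scheduled outcomes, or resolved between visits, notably between day 28 and week 24. This should be corrected, because events lost at recording cannot be restored, but it does not threaten the main results.

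**What to change.** - In 4.6.1.1 and 4.6.1.2, require at least every oral or surgical-site adverse event from Visit 3 to Visit 7 to be recorded, in all three arms, whatever its cause.
- Capture causality as a separate CRF field with non-overlapping levels (for example not, possibly, probably and definitely related). Word the levels to refer to the procedure and any study material, so that Bio-Gide and the allograft are covered on the same terms as GUIDOR.
- Delete the exemption for events with another possible cause.
- Summarize all recorded events by group first, then the related subset.
- Reconcile the synopsis line with the list of expected events that are not captured. Otherwise the promise of all adverse events would still not match the data.

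The cost is protocol and CRF wording, plus a few more event lines in 60 subjects who are already asked an open health question at each visit. The downside is small: some minor unrelated events will be recorded and will need monitoring.

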4.6.1.2 Recording of Adverse Events and Adverse Device Effects

At each visit, the subject will be asked an open question; "Have you had any health problems since the previous visit?"

All health problems, reported by the subject or found at the clinic visit, where the investigator believes the event to be related to the investigational medical device or treatment, must be recorded in the CRF as AEs, specifying time of onset, action taken, outcome and whether it constitutes a SAE or not.

Should a pregnancy occur, it must be reported in accordance with the procedures described in Section 9.2, Pregnancy. Pregnancy in itself is not regarded as an AE unless there is a suspicion that a medical device under study may have interfered with the effectiveness of a contraceptive medication.

4.6.1.3 Reporting of Serious Adverse Events

Timelines for reporting of SAEs

Investigators and other study site personnel should inform the IRB of serious adverse events per the IRB reporting requirements. It is recommended that serious adverse event be entered into the eCRF within 24 hours upon awareness of the event.

4.7 Protocol Deviations

The investigator should avoid deviating from the protocol. All deviations related to clinical investigation inclusion or exclusion criteria, conduct of the investigation, patient management, or patient assessment are to be documented on the eCRF provided for that purpose. Notification to the IRB should be documented and maintained in the clinical investigation file (as required).

4.8 Genetics

Not applicable

5 DATA MANAGEMENT

5.1 Data handling

Paper case report forms will be utilized for the study. The CRF will be completed for each included patient. The completed CRFs will not be made available in any form to third parties. The data will be reviewed by the monitor or designee and queries will be issued. The study site personnel are required to resolve any such queries.

At the end of the study, the monitor will perform final validation checks, after which Clean File will be declared.

5.2 Record retention

To enable evaluations and/or audits the investigator agrees to keep records in the Investigator's Study File (ISF), including the identification list of the participating patients, all original signed Informed Consent forms, and detailed records of medical device disposition. The investigator will maintain complete, accurate and current study records during the study and for 10 years after the later of the date on which the study is terminated or completed, or the date the records are no longer required.

6 STATISTICAL METHODS AND DETERMINATION OF SAMPLE SIZE

6.1 Statistical evaluation – general aspects

A comprehensive Statistical Analysis Plan (SAP) may be prepared before database lock. When using the terminology descriptive statistics it means that number of patients, mean, median, standard deviation, minimum and maximum values will be presented for continuous data and frequencies and percentages for categorical data.

If nothing else is stated, descriptive statistics will be given for each variable in the study and p-values may be complemented by confidence intervals as appropriate. All p-values presented will be two-sided. A p-value less than 5% will be called “statistically significant” but all conclusions will be based on the primary objective and hence multiplicity is accounted for even though careful interpretations are necessary as multiple tests are performed.

Analysis populations are defined as follows:

- The Intent-to-Treat (ITT) population includes all enrolled subjects who underwent guided bone regeneration procedure.
- The Per-Protocol (PP) population includes all enrolled subjects who had successful guided bone regeneration procedure and no major protocol deviations (defined as inclusion/exclusion or informed consent violations.)

The ITT population will be the primary analysis population for all endpoints. Analyses on the PP population will be supportive of the ITT analyses.

Demographics and other baseline characteristics

Demographics and other baseline characteristics will be presented by means of descriptive statistics (by group and in total). Continuous variables will be presented by means of number of observations (N), minimum (min), median, maximum (max), mean, and standard deviation (std). Discrete variables will be presented by frequency and percentage.

Covariates and prognostic variables

No covariates are judged to influence the outcome of the primary or any of the secondary variables.

Handling of dropouts and missing data

Patients dropping out from the trial prior to study end will not be replaced. Data totally missing will not be estimated.

Multicenter

This study is a multicenter study. However, there is not a priori reason to suspect that there will be any qualitative differences between the centers regarding any of the efficacy variables nor regarding the safety variables. Therefore, the primary statistical analyses will not include center in the model.

In order to harmonize the use and handling of the graft materials, training will be conducted prior to study start at each center.

Subgroup analyses

No subgroup analyses are planned.

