2 STUDY OBJECTIVES

2.1 Primary objective

The primary objective is to compare the horizontal and vertical changes in osseous dimension of a single bound edentulous zone following guided bone regeneration. Three different bone augmentation techniques will be used. Data will be obtained from DICOM images acquired by CBCT imaging. The dimensional location of the facial bone plate in the Z-axis and Y-axis will be reported in terms of a reference point (the mid-alveolar point positioned on a tangent drawn from the cementoenamel junctions of the mesial and distal adjacent teeth. The changes from baseline to six months will be compared.

Hypothesis: The treatment group with GUIDOR membrane with allograft is superior to comparative treatment groups (GUIDOR membrane alone or Bio-Gide® membrane with allograft).

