6.2 Method of statistical analysis

Primary objective

The primary objective is to compare dimensional bone changes from baseline (Visit 2) to six months (Visit 7) occurring in a single bound edentulous space following alveolar bone regeneration using three different techniques.

Assume the change (in the mid-buccal horizontal bone dimensions from baseline to six months) is denoted C_A , C_B and C_C , for group A, B and C, respectively. The null-hypotheses (two) is then to test if:

$$H_0: C_A = C_i \quad (i = B \text{ and } C, \text{ respectively})$$

can be rejected and hence

$$H_1: C_A \neq C_i \quad (i = B \text{ and } C, \text{ respectively})$$

accepted.

H_0 will be tested by means of the Wilcoxon rank sum test. A p-value less than 5% will be regarded statistically significant.

Secondary objectives

Secondary objectives of the study are to evaluate and compare clinical healing parameters between different grafting techniques (i.e. to compare between groups A, B, and C):

- Inflammation by assessing the presence or absence of soft tissue erythema within 3 mm from the crestal incision at 1 week, 2 weeks, 4 weeks, and 6 months following bone augmentation. The chi-squared analysis will be used.
- Infection by determining the presence or absence of suppuration or soft tissue fluctuance at 1 week, 2 weeks, 4 weeks, and 6 months following bone augmentation. The chi-squared analysis will be used.
- Soft tissue complications by determining the presence or absence of membrane exposure or soft tissue dehiscence at 1 week, 2 weeks, 4 weeks, and 6 months following bone augmentation. The chi-squared analysis will be used.

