6.3 Determination of sample size

A sample size of 20 participants per treatment group was selected following power calculations and allowing for 10% patient dropout. A sample size of 18 patients was calculated for the primary outcome variable (horizontal bone changes) with the assumption that the detectable difference would amount to 0.5 mm with a standard deviation of 0.5. The type I error probability was set at 0.05 and the statistical power was set at 80%.

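### Section 6.1 says multiplicity is accounted for, but the primary objective holds two unadjusted 5% tests (A vs B, A vs C) and no success rule

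*Combined protocol and SAP*

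**What the plan says.** Section 6.1 makes all p-values two-sided at 5% and then says that "conclusions will be based on the primary objective and hence multiplicity is accounted for even though careful interpretations are necessary as multiple tests are performed". It names no adjustment method. It adds that "A comprehensive Statistical Analysis Plan (SAP) may be prepared before database lock", so a later document that could settle the matter is optional.

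Section 6.2 gives the formal test for change in mid-buccal horizontal dimension: "The null-hypotheses (two) is then to test if" group A equals group B and, respectively, group C. Both use the Wilcoxon rank sum test, and "A p-value less than 5% will be regarded statistically significant".

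The nearest thing to a success rule is the hypothesis in section 2.1, that GUIDOR with allograft "is superior to comparative treatment groups (GUIDOR membrane alone or Bio-Gide® membrane with allograft").

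Section 6.3 sizes the trial: "A sample size of 18 patients was calculated for the primary outcome variable (horizontal bone changes"), for a 0.5 mm difference with SD 0.5, and 20 per group are enrolled to allow for 10% dropout. "The type I error probability was set at 0.05 and the statistical power was set at 80" percent. It does not say which comparison, or how many, the power refers to.

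**The concern.** Resting conclusions on the primary objective deals with multiplicity between primary and secondary analyses. It says nothing about multiplicity within the primary objective, where section 6.2 has two tests. The inference drawn in 6.1 therefore does not follow, and the warning about careful interpretation controls no error rate.

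What is at stake is the meaning of a mixed result. Section 2.1 can be read in three ways: one significant comparison supports the hypothesis, both are needed, or there are two separate conclusions. If A beats B but not C, or the reverse, these readings give different answers, and nothing in the plan obliges anyone to choose before the results are known.

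**Working it through.** **Inputs.** From 6.3: difference 0.5 mm, SD 0.5 (standardised effect 1.0), alpha 0.05, power 80%, 18 evaluable and 20 enrolled per group. From 6.1 and 6.2: two-sided Wilcoxon tests, A vs B and A vs C, each at 5%. From 3.1: equal groups. Assumed: normal data with equal SDs.

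**1. The plan's own figure.**
- Normal approximation: n = 2(1.960 + 0.842)² × (0.5/0.5)² = 15.7, so 16.
- Two-sample t-test: 16.7.
- Wilcoxon efficiency under normality (multiply by π/3): 16.7 × 1.047 = 17.5, so 18.
- Dropout: 18/0.9 = 20.

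The stated 18 and 20 reproduce for one two-sided comparison at an unadjusted 5%. Simulated Wilcoxon power is 80% at 18 and 85% at 20.

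**2. Reading 1: either significant comparison is enough.** Under the global null:
- Independent tests: 1 − 0.95² = 9.75%.
- The tests share group A. With equal groups, the covariance of the two mean differences is σ²/n and each variance is 2σ²/n, so the correlation is 0.5. The bivariate normal then gives 9.07%.
- Exact Wilcoxon, simulated with a shared group A: 8.6% at 18 and about 9% at 20. One such test has an exact size of 4.71% and 4.91%.
- Section 2.1 is directional. The chance of at least one false finding in favour of A is about 4.3% at 18 and 4.4% at 20, against 2.35% and 2.45% for one test.

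If A truly differs from one comparator, only the other test can err, at its own 4.7% to 4.9%.

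**3. Reading 2: both must be significant.** Error stays at or below 5%. Power for both:

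| True differences | 18 per group | 20 per group |
|---|---|---|
| 0.5 and 0.5 mm | 69% | 76% |
| 0.75 (assumed) and 0.5 mm | 80% | 85% |

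In the first row, exactly one test is significant in about 23% (18 per group) or 19% (20 per group) of trials. A mixed result is thus quite likely even when A is better than both comparators.

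**4. Reading 3: two separate conclusions.** Each has its own 5% error, and the 80% in 6.3 applies to each. The chance of at least one error across the two is as in step 2, so multiplicity across them is not accounted for.

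**5. Holm as a remedy.** Under the global null, the chance of any rejection is about 4.5% at 18 and 4.6% at 20. Power per comparison:

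| True differences | Unadjusted, 18 / 20 | Holm, 18 / 20 |
|---|---|---|
| Both 0.5 mm | 80% / 85% | 77% / 82% |
| One 0.5 mm, the other zero | 80% / 85% | 72% / 77% (for the real difference) |

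**The case against.** The strongest reply is that these are two different questions. A vs B holds the membrane fixed and varies the allograft. A vs C holds the allograft fixed and varies the membrane. Section 6.2 writes two nulls, each with its own alternative. Whether distinct questions in a three-arm trial need familywise control is a disputed design choice. With separate conclusions, a mixed result has a plain meaning and the power statement stands. This is a legitimate position, and the fix must allow it. But the plan does not adopt it: 2.1 states one hypothesis and 6.1 claims that multiplicity is handled. Under separate conclusions that claim is what has to go.

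A reader might infer that the trial runs a 9% type I error. The documents do not support that. It needs an either-counts rule, which no section states, and both nulls true. Section 1.2 expects a difference, most of all between grafted and control sites.

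A reader might also infer that the 80% power or the sample size is wrong. Neither is: both are right for one unadjusted comparison. Even if both tests are required, joint power is 80% at 18 when one difference is 0.75 mm (assumed).

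Finally, 6.1 openly warns that several tests are run and allows a SAP before database lock. This softens the point, but the SAP is optional and the warning sets no rule.

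**Conclusion.** The concern stands in a limited form. The statement in 6.1 that multiplicity is accounted for is unsupported, because it covers the secondary tests and not the two primary ones, and the decision rule for those two is missing. It should be fixed.

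The size is conditional on the reading: about 9% for any false rejection (about 4.4% in favour of A) if either comparison suffices and both nulls hold; controlled error with 69% to 80% joint power at 18 per group if both are required, over the two effect scenarios shown; nominal 5% and 80% for each if the conclusions are separate. These figures concern horizontal change only and rest on normal data with the SD of 0.5 from 6.3. The 0.75 mm scenario is an assumption, not a value in the plan.

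**What to change.** Replace the sentence in 6.1 with one rule, fixed before data are seen:

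- (a) Holm over A vs B and A vs C, which makes the present claim true.
- (b) A fixed sequence at 5%, with the order justified. The second comparison is tested only if the first is significant, so its power is the joint power above.
- (c) Success only if both are significant at 5%.
- (d) A statement that the two comparisons are separate conclusions, each at 5% without familywise control, with the claim about multiplicity deleted.

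In 6.3, say that 80% at 18 per group is for one unadjusted comparison, and give power under the chosen rule with its assumed differences.

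**Cost.** Wording in 6.1, 6.2 and 6.3, with no added patients or visits if the lower stated power is accepted. Option (d) loses no power but gives up the claim. Holm costs about 3 points per comparison if both differences are 0.5 mm and about 8 points if only one is real. Under (c), power is the joint figure.

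**Separate item.** Section 2.1 says "The primary objective is to compare the horizontal and vertical changes in osseous dimension", and the synopsis likewise makes both dimensions primary, while 6.2 and 6.3 test and size horizontal change only. These should be reconciled, for example by naming horizontal change, the variable that was sized, as the single primary variable. If vertical change stays primary, the chosen rule must cover it too, which would lower power further.
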